### 13.0 SURGICAL GUIDELINES

Timing of protocol therapy administration, response assessment studies, and surgical interventions are based on schedules derived from the experimental design or on established standards of care. Minor unavoidable departures (up to 72 hours) from protocol directed therapy and/or disease evaluations (and up to 1 week for surgery) for valid clinical, patient and family logistical, or facility, procedure and/or anesthesia scheduling issues are acceptable (except where explicitly prohibited within the protocol).

#### 13.1 Neurosurgical Procedures

There are no standard neurosurgical procedures for high-grade astrocytomas. An attempt should be made to perform maximal safe surgical resection. The extent of surgical resection will depend upon the location and growth features of the tumor. It is suggested that navigational guidance (stereotaxy, intra-operative MRI, ultrasound) be used in an effort to guide surgical resection. Patients potentially eligible for this study must undergo at least tissue sampling that results in a pathologic interpretation. **No patient will be eligible for this study without a pathological diagnosis.**

#### 13.2 Definitions of Extent of Resection

**Note:** An attempt should be made to estimate the volume of the residual tumor in cm^3.

##### 13.2.1 Biopsy Only

An open surgical removal or close (e.g., needle) removal of tissue for the sole purpose of making a pathologic diagnosis. If tumor removal is less than 10% of the total tumor mass, this will be considered a biopsy only.

##### 13.2.2 Partial Resection

The surgical removal of greater than 10% but less than 50% of the tumor mass.

##### 13.2.3 Subtotal Resection

The surgical removal of greater than or equal to 50% but less than 90% of the tumor mass.

#### 13.2.4 Near Total Resection (Extensive Subtotal Resection)

Resection of greater than or equal to 90% of the tumor mass, but residual disease apparent on inspection.

#### 13.2.5 Gross Total Resection

Resection of all visible tumor.

### 13.3 **Imaging Confirmation of Extent of Resection**

See [Section 16.0](#) for Neuroimaging Guidelines. All patients must have confirmation of the neurosurgical staging of the extent of resection with a post-operative MRI with and without contrast. It is strongly encouraged that the post-operative imaging of the brain be done within 48 hours of surgery if possible, but if unable to be done at that time (or post-operative changes obscure potential residual tumor) must be done prior to enrollment. The requirement for a post-operative MRI is waived for patients who undergo biopsy only.

### 13.4 **Peri-operative Corticosteroids**

Some patients with large tumors may require initiation of corticosteroid therapy pre-operatively to reduce associated cerebral edema or improve neurologic function.

Usual corticosteroid dosage is 0.25 to 1 mg/kg/day of dexamethasone in divided doses every 6–12 hours. Corticosteroids may be discontinued during the peri-operative period; however, every attempt should be made to taper and discontinue corticosteroid therapy as soon as clinically feasible (7 days).

## 14.0 **PATHOLOGY GUIDELINES AND SPECIMEN REQUIREMENTS**

**Before entering patients on this trial, clinicians should discuss this protocol with their pathologist and provide them with the APEC14B1 protocol and list of the required materials that will need to be submitted for the rapid central pathology screening review.**

It is the responsibility of the Principal Investigator at the institution to ensure that the pathologist is informed and to request that all HGG patient specimens be forwarded to the COG Biopathology Center (BPC), as required. The BPC will NOT request materials.

### 14.1 **Required Rapid Central Pathology Review**

**See APEC14B1 and [Section 3.1](#) for required materials for the Rapid Central Screening Review.**

The pathologic classification of tumors is becoming increasingly complex since there is considerable variation in the histological features of patients. Central review is therefore critical to ensuring that the diagnosis is accurate and that patients are treated appropriately. Central pathologic review will be performed on all diagnostic specimens (whether resected or biopsied). The classification and grading of the tumors will be performed according to the 2016 WHO Central Nervous System (CNS) criteria. The submission of pathology material shall be made directly from the participating institutions. Results of the review will be given to the treating institution.

If there is a discrepancy between the institutional diagnosis and the diagnosis on the rapid screening central review of a patient, then a discussion between the local and study pathologists will take place to attempt to reach a consensus, however, the decision of the study pathologists will be used to confirm eligibility. At least ONE of the central review pathologists will need to confirm eligibility prior to enrollment. Slides will be stored at the COG BPC for quality control purposes.

## 15.0 SPECIAL STUDIES SPECIMEN REQUIREMENTS

### 15.1 Required Studies

#### 15.1.1 Rapid Central Molecular Screening Review

In patients who have pathology confirmed by central pathology review, Rapid Central Molecular Screening Review will be performed on genomic DNA extracted from FFPE tissue. See [Section 3.1.1.4](#) for details. These specimens are submitted via APEC14B1.

### 15.2 Optional Studies

#### 15.2.1 Genomic Analysis of Germline DNA

Genomic analysis of germline DNA will be performed in consenting patients. If a patient has consented to optional banking on APEC14B1, we will request use of some of the banked blood sample to study germline DNA on ACNS1721. **If a patient has not submitted a banked blood sample on APEC14B1 but consents to correlative biology studies on ACNS1721, please collect a peripheral blood sample before treatment begins.** Leftover samples will be banked at the COG Biopathology Center.

##### 15.2.1.1 Specimen Requirements

At pre-treatment, please collect 4–10 mL of peripheral blood, **preferably** in a 10 mL *Streck* Cell Free DNA tube. Purple top EDTA tubes may be used if *Streck* tubes are not available at the institution. Please note that *Streck* tubes will not be provided for ACNS1721 correlative studies. Samples should be collected prior to beginning protocol therapy, but can be collected within the first 5 days of treatment if needed.

Note: A minimum of 5 mL of blood is required if using *Streck* tubes to maintain sample integrity.

##### 15.2.1.2 Specimen Processing

The blood should be shipped whole and unprocessed to the BPC on the day of collection. If a specimen cannot be shipped the day of collection, then blood in EDTA tubes should be kept at 4°C while blood in *Streck* tubes must be kept at room temperature. Ship blood on the next working day.

15.2.1.3 Specimen Labeling and Shipping

Use a waterproof marker to label the tube with the COG patient ID number, BPC number, specimen type (blood), and the collection data.

The BPC provides a shipping label to sites in North America. Please access the BPC Kit Management system at <https://kits.bpc-apps.nchri.org> to print a shipping label. Blood may be shipped Monday through Friday for receipt on Tuesday through Saturday. If blood is shipped on a Friday, please check “Yes” for Saturday delivery.

Include a Specimen Transmittal Form with each shipment.

Please ship blood in EDTA tubes on a cold pack during warm months. Blood collected in *Streck* tubes should not be shipped with a cold pack. Samples should be shipped by FedEx Priority Overnight to:

15.2.2 Genomic, Transcriptomic, and Epigenetic Analysis

In consenting patients, please submit peripheral blood and frozen tumor for the biology studies as outlined in the table below.

15.2.2.1 Specimen Schedule and Requirements

Samples should be collected as outlined below and shipped to the [name] Lab (see [Section 15.2.2.3](#)):

Sample	Amount	Container	Taken at the following time points:
Peripheral blood	5–10 mL per timepoint	Streck Cell-Free DNA tubes preferred . Purple top EDTA tubes may be used if Streck tubes are not available.	
 
• Pre-treatment/diagnosis
 
• At the first MRI post-Chemoradiotherapy
 
• At the end of treatment MRI
 
• During follow-up with the 6, 12, 20, and 30 month MRI (see Section 7.3)
 

Frozen tumor	Any amount available	Cryovial or Eppendorf tube, without media	Tumor resection (at time of diagnosis)

Note: A minimum of 5 mL of blood is required if using 10 mL *Streck* tubes to maintain sample integrity.

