## 2.8 Genomic, Epigenomic, and/or Transcriptomic Analysis

Mutational screening for known recurrently mutated oncogenes and tumor suppressors in pediatric high-grade glioma, including but not limited to *PTEN*, *TP53*, *PDGFR*, *PI3K*, *BRAF*, *IDH1/2*, *H3F3A*, *HIST1H3B*, *SETD2* and *ATRX/DAXX*, as well as mutations conferring DNA repair defects sensitizing to PARP inhibition including but not limited to *BRCA1/2*, *RAD51*, *ATM*, and *FANCA1/2*, using either targeted sequencing or whole exome/genome sequencing or transcriptome analysis will be performed on DNA or RNA from tumor tissue. We hypothesize that patients with sensitizing mutations to PARP inhibition may have improved outcome compared to those with wild-type tumors.

Depending on tissue availability, we will perform additional genomic (targeted sequencing, whole genome sequencing, whole exome sequencing), epigenomic (ChIp-Seq, Whole Genome Bisulfide Sequencing, HiC-Technology), and transcriptomic (RNA sequencing) investigations to correlate the profile of potential alterations or epigenetic signature with therapeutic responses. This may help identify other relevant alterations that could be used in the future as molecular signature to evaluate potential responders at study enrollment. To this effect, we will use additional genomic, epigenomic, and/or transcriptomic analyses to identify methylation class, gene expression, mutations, and gene fusions. Whenever possible, germline DNA analysis will be performed in parallel to aid in somatic mutation calling and to identify underlying germline tumor predispositions (optional study). We will also assess whether mutational profiles/oncogenic drivers can be identified in the plasma. To this effect, we will use circulating tumor nucleic acids (ctDNA) extracted from the plasma to investigate if the presence of genetic alterations identified in the above described analysis can be used as biomarkers. The purpose of these correlative studies will be to assess whether plasma from these patients can be used as a surrogate marker of the tumor in order to monitor disease progression/regression and/or response to therapy.

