**7.3 End of Therapy & Follow-up**

STUDIES TO BE OBTAINED	End of Therapy	Every 3 months for Year 1 (i.e., 3, 6, 9, 12 months)	Every 4 months for Year 2 (i.e., 16, 20, 24 months)	Every 6 months for Year 3 (i.e., 30, 36 months)	Once yearly for Years 4–10
Physical Exam with VS	X				
Ht, Wt, BSA	X				
CBC, differential, platelets	X				
Creatinine, bilirubin	X				
AST/ALT	X				
Brain MRI	X	X	X	X	X
Tumor and biology samples (in consenting patients, see Section 15.2.2 )	X	X (at 6 and 12 months)	X (at 20 months)	X (at 30 months)	

The table above indicates required End of Therapy evaluations and required Follow-Up imaging scans. In addition, see COG Late Effects Guidelines for recommended post treatment follow-up: <http://www.survivorshipguidelines.org/>

**Note:** End of Therapy data should be submitted per the Case Report Forms (CRFs) schedule.

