### 16.1 Timing of MRIs and Retrospective Central Imaging Review

Sites are required to submit imaging scans for retrospective central imaging review. To document the initial extent and degree of residual tumor, standard whole brain MRI with and without contrast (gadolinium) must be performed at the following time points:

1. Brain MRI: Pre- and post-operative\* MRIs should be performed prior to enrollment onto the study
2. Brain MRI: Prior to each odd-numbered cycle of Maintenance chemotherapy
3. Brain MRI: At the end of therapy
4. Brain MRI: Every 3 months for Year 1 in follow-up (3, 6, 9, 12 months)
5. Brain MRI: Every 4 months for Year 2 in follow-up (16, 20, 24 months)
6. Brain MRI: Every 6 months for Year 3 in follow-up (30, 36 months)
7. Brain MRI: Once yearly for Years 4–10 in follow-up
8. Brain MRI: At progression/relapse (if outside the timepoints noted above)

\*It is strongly encouraged that the post-operative brain MRI be done within 48 hours of surgery if possible, but if unable to be done at that time (or post-operative changes obscure potential residual tumor) must be done prior to enrollment. The requirement for a post-operative MRI is waived for patients who undergo biopsy only.

Tumor response assessment will be performed at each site. For all patients, submit all MRI studies with their corresponding reports to the address in [Section 16.5](#). Please note that results from the retrospective central imaging review will not be returned to the site.

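### No blood draw is tied to the MRI that shows progression, so about half of post-therapy progressions in Stratum 2 would lack a concurrent plasma sample even in the best case

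*Combined protocol and SAP*

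**What the plan says.** Section 2.8 gives the purpose of the plasma work: to find out whether plasma can act as a "surrogate marker of the tumor in order to monitor disease progression/regression and/or response to therapy".

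The specimen table in Section 15.2.2.1 lists the peripheral blood draws: before treatment, at the first MRI after chemoradiotherapy, "At the end of treatment MRI", and "During follow-up with the 6, 12, 20, and 30 month MRI". The follow-up table in Section 7.3 agrees: "X (at 6 and 12 months") in Year 1, then months 20 and 30, and nothing in Years 4–10.

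Imaging follows a fuller schedule. Section 16.1 sets MRIs at months 3, 6, 9, 12, 16, 20, 24, 30 and 36 of follow-up, then yearly to Year 10. Item 8 adds a scan "At progression/relapse (if outside the timepoints noted above"). Neither specimen table attaches blood to that scan.

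Sampling is optional (Sections 7.2 and 15.2.2). Section 9.5 plans a descriptive analysis of the longitudinal plasma: the percentage of patients with samples, and changes in molecular markers.

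**The concern.** To judge whether plasma tracks progression, one needs the marker value when imaging shows progression. Here the reference measurement (MRI) is triggered by the event, but the marker measured against it is not. Followed exactly, the plan obtains a concurrent value after therapy only when progression happens to be found at one of four scans.

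This matters most in Stratum 2, the only stratum still open to accrual. Planned therapy lasts just under a year and control PFS at 1 year is 85.4%, so most of its progressions are expected after therapy, where the gap lies. With 30 patients there are few progressions, and each unsampled one is a real loss. A later fixed draw may not make it good: it may follow new treatment, and joining another COG therapeutic study at recurrence takes the patient off study (Section 8.2e).

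**Working it through.** The documents give no figure for plasma coverage at progression, so there is none to reproduce. The PFS inputs can be checked. With S^HR at HR 0.45, 0.854^0.45 = 0.931 (+7.7 points) and 0.611^0.45 = 0.801 (+19.0 points). These match the gains of about 8% and 19% stated in Section 9.2.

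**Inputs**
- Stratum 2 control PFS of 85.4%, 61.1% and 35.8% at 1, 2 and 5 years; HR 0.45; 30 patients (Sections 9.1 and 9.2).
- Planned therapy (Section 4.1): 6–7 weeks of RT + 4 weeks of rest + 10 × 4 weeks = 50–51 weeks, or 11.5–11.7 months; 11.6 is used below.
- MRI schedule from Section 16.1; draws from Sections 7.3 and 15.2.2.1.

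**Simple count.** Through month 36, 4 of 9 scheduled follow-up MRIs carry a draw. Through month 120 it is 4 of 16.

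**Weighted by the plan's PFS.** Assumptions: constant hazard between the stated PFS points; PFS time and therapy start together; follow-up months count from the end of planned therapy; each progression is found at the next scheduled MRI.

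Monthly hazards under control PFS:
- Year 1: −ln(0.854)/12 = 0.01315
- Year 2: −ln(0.611/0.854)/12 = 0.02790
- Years 2–5: −ln(0.358/0.611)/36 = 0.01485

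PFS at the end of therapy is exp(−0.01315 × 11.6) = 0.859.

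| Follow-up MRI (month) | PFS at that scan | Progressions found (% of all patients) | Blood drawn |
|---|---|---|---|
| 3 | 0.794 | 6.4 | no |
| 6 | 0.730 | 6.4 | yes |
| 9 | 0.672 | 5.9 | no |
| 12 | 0.618 | 5.4 | yes |
| 16 | 0.579 | 3.9 | no |
| 20 | 0.546 | 3.3 | yes |
| 24 | 0.514 | 3.1 | no |
| 30 | 0.470 | 4.4 | yes |
| 36 | 0.430 | 4.0 | no |

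Paired: 6.4 + 5.4 + 3.3 + 4.4 = 19.5.
- Through month 30: 19.5/38.8 = 50%.
- Through month 36: 19.5/42.8 = 46%.

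The same steps at HR 0.45 give 11.4 paired, out of 22.1 through month 30 (52%) and 24.9 through month 36 (46%).

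**Counts, if all 30 patients consent, through month 36**
- Control PFS: 30 × 0.428 = 12.8 post-therapy progressions, 30 × 0.195 = 5.8 paired.
- HR 0.45: 30 × 0.249 = 7.5 progressions, 30 × 0.114 = 3.4 paired.

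**Sensitivity**
- Moving 5-year PFS by its standard error of 11.4 points either way (24.4% to 47.2%) gives 49–52% through month 30 and 45–47% through month 36.
- If 20% to 50% of progressions are found off schedule (an assumed range), the month-36 share becomes 0.46 × 0.8 = 37% down to 0.46 × 0.5 = 23%.
- Through month 120 the share is 21–27% if the 2–5 year hazard continues, or 38–39% if no events occur after year 5.

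**All Stratum 2 progressions, on therapy and after, through month 36.** On-therapy progressions are counted as covered by the end-of-treatment draw.
- Control PFS: (14.1 + 19.5)/(14.1 + 42.8) = 59%.
- HR 0.45: (6.6 + 11.4)/(6.6 + 24.9) = 57%.

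**The case against.** The case for leaving the schedule alone has substance.

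- Objectives 1.2.1–1.2.4 do not mention plasma or progression monitoring. That purpose stands only in Section 2.8, where it also covers response to therapy. The baseline, post-chemoradiotherapy and end-of-treatment draws serve the response part. This stands.
- The study is optional and the planned plasma analysis descriptive. No estimate of plasma positivity at progression is planned, and no primary-endpoint figure is affected. This stands and limits the importance of the point. Even so, a descriptive display of marker change needs values at progression to say anything about monitoring.
- Progression on therapy ends protocol therapy (Section 8.1a) and so leads to the end-of-treatment draw. This stands. In Stratum 1, where control PFS at 1 year is 42.6%, most progressions would fall in that period.
- Fixed-time draws taken before progression can show whether plasma changes ahead of imaging. This is a fair merit, but without a value at progression there is often nothing to set those earlier values against.
- Subsection 15.2.2.4 is not in the copy of the document used here. The table in 15.2.2.1 reads as a full list of time points, Section 7.3 matches it, and the remaining text mentions no progression sample.

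A reader might infer that the study cannot estimate plasma status at progression at all, or that nearly all progressions go unsampled. The documents support neither reading: in the best case 57–59% of all Stratum 2 progressions through month 36 would be paired.

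**Conclusion.** The gap is real and its consequence moderate. The schedule does not serve the progression-monitoring part of the aim well once therapy has ended. On the plan's own PFS figures, with every progression found on a scheduled scan and every draw made, about half of Stratum 2 post-therapy progressions have a concurrent sample through month 30 and about 46% through month 36. That is roughly 3–6 of 7–13 progressions with full consent. Incomplete consent lowers the counts; off-schedule detection or missed draws lower the share as well. After month 30 none is covered.

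The result would rest on a handful of patients whose progression happened to coincide with a draw, so it would be imprecise rather than unobtainable. The primary analysis is untouched. This is a cheap improvement to an exploratory study, not a flaw in the trial's main design.

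**What to change.** In Sections 15.2.2.1 and 7.3, for consenting patients, add a peripheral blood draw at the MRI that first shows progression or relapse, whether scheduled or under Section 16.1 item 8. Take it before any new anti-tumor therapy, and let it replace that patient's next scheduled follow-up draw. In Section 9.5, add a summary of plasma marker status at progression against the patient's last progression-free sample. Every post-therapy progression within the rule then has a planned concurrent sample, before missed draws.

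The cost is an amendment to the two tables and the optional-study consent text, and one 5–10 mL draw moved to a visit the patient already attends. Up to month 30, each progressing patient loses one fixed-time post-progression sample.

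After month 30 no scheduled draw remains to be replaced. The amendment should therefore either limit the rule to progression found by month 30 or say plainly that later progression adds one draw.

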### 15.2.2.2 Specimen Preparation

Note: Frozen samples (tissue, plasma, buffy coat) may be stored for up to 6 months at -80°C. Samples should not be batched.

#### 15.2.2.2.1 Peripheral Blood

Whole blood should be collected **preferably** in 10 mL *Streck* tubes (Cell-Free DNA BCT®). If *Streck* tubes are not available at the institution, K2 EDTA (BD Vacutainer®) tubes can be used and the same centrifugation steps followed. Please note that *Streck* tubes will not be provided for ACNS1721.

Whole blood should be separated into plasma and blood cells by two consecutive centrifugations:

1. Centrifuge at 800g (2900 rpm) at +4°C for 10 minutes to separate blood, buffy coat, and plasma.
2. Remove the top layer of plasma and place in an Eppendorf tube in 1.5 mL aliquots for subsequent centrifugation (Step 5).
3. Remove “buffy coat” (concentrated leukocyte band) and store in plastic screw-cap (cryo)vial or Eppendorf tube at -80°C.
4. Store the lower layer of blood in a separate plastic screw-cap (cryo)vial or Eppendorf tube at -80°C.
5. For the second centrifugation step, centrifuge the supernatant (plasma) from Step 2 at 21000g (15,000 rpm or the maximum speed available) at +4°C for 10 minutes.
6. Remove the resulting supernatant (plasma) and store in a cryovial in 2 mL aliquots at -80°C.

*Optional:* The pellet from the centrifugation at Step 5 can be combined with the buffy coat from Step 3.

#### 15.2.2.2.2 Frozen Tumor Sample

Frozen tumor samples should be stored in a cryovial or Eppendorf tube, without media.

### 15.2.2.3 Specimen Labeling and Shipping

**Please contact the [name] Lab at [REDACTED] before specimens are shipped to obtain a FedEx account number.** Specimens should be labeled with the patient ID, tumor location (if applicable), and date and time of collection. For plasma, please note the

time from collection to sample processing if possible. Specimens should be shipped frozen on dry ice to the receiving institution. Ship specimens for overnight, Tuesday through Friday delivery only, with the institutional pathology report, diagnosis, age, and gender of the patient to:

15.2.2.5 Methodology at the [name] Lab

**Note:** If the patient consented to banking, then any leftover specimens will be sent from the [name] Lab to the COG Biopathology Center for banking.

15.2.2.5.1 **Plasma**

Cell-free circulating DNA (cfDNA) will be isolated from approximately 2.5 mL of plasma obtained from centrifugation of ~5 mL of blood. RNase H-dependent PCR (rhPCR), which is an amplification step specific for mutant copies of genes of interest, will be performed on the isolated DNA. Digital droplet PCR (ddPCR) will be performed on a portion of the resulting products to analyze the presence of mutant and wild-type copies of the genes of interest. Alternatively, direct NGS can be performed on the cfDNA, depending on the quantity and quality of material.

15.2.2.5.2 **Tumor**

DNA and RNA will be extracted from frozen tumor tissue for genomic, transcriptomic, and epigenetic analysis such as Whole Blood Exome Sequencing, Whole Genome Sequencing, Whole Genome Bisulfide Sequencing, transcriptome, and methylation, among other techniques.

